Statistical Analysis Plan: AVTX-002-NEA-201

Study Title:	A Phase 2, Randomized, Double-Blind, Placebo-Controlled, Parallel Group Study to Evaluate the Safety and Efficacy of AVTX-002 for the Treatment of Poorly Controlled Non-Eosinophilic Asthma
Study Number:	AVTX-002-NEA-201
Study Phase:	2
Sponsor:	Avalo Therapeutics, Inc. [name] [name]
NCT #:	NCT05288504
Version:	Final 4.0
Date:	02 Jun 2023

Confidentiality Statement

This document contains confidential and proprietary information, and is not to be distributed to any third party.

Version History	
Version: Final 1.0	Initial version
Version: Final 2.0	
Updates resulting from Protocol Amendment No. 4 (ie, Protocol Version 5.0, 17 Oct 2022)
 
Updates made to baseline definitions as well as post-baseline calculations for diary data
 
Updates made to reflect programmatically determined derivation of the occurrence of asthma related events, in addition to the Investigator assessment in the eCRF
 
Updates made to reflect repeat analysis of the primary endpoint based on different baseline values for daily number of SABA puffs/inhalations and peak flow rate.
 
Updates made to include calculation of an annual asthma related event rate for each treatment group
 
Added production of figures to display results for peak flow rate and number of SABA puffs/inhalations recorded by subjects in their diary
 
Addition of a Per Protocol Analysis Set
 
Added clarification on handling of clinical laboratory results reported as not fully numeric
 
Addition of PCI criteria for vital signs

Version: Final 3.0	
Addition of statistical comparison between treatment groups for time to first asthma related event, as well as addition of a Kaplan-Meier plot of the time to asthma related event curves of the two treatment groups.
 
Addition of repeat of the primary efficacy analysis for subjects with an asthma related event in the period of time from date of first administration of study drug through 28 days after final dose of study drug
 
Update to wording for further clarity on the start date of an asthma related event
 
Addition of clarification of asthma related event criterion related to use of systemic corticosteroids
 
Minor corrections to formatting

Version: Final 4.0	
Update to Section 6.2.4 for imputation of missing values and derivation of overall score for the Asthma Control Questionnaire
 
Update to Section 10.3 to add that the screening eosinophil level will be part of the subject listing as well as table summary for demographics and baseline characteristics
 
Update to Section 10.6.1 to add that Wald Ztest will be performed including and without continuity correction
 
Update to Table 4 (Appendix 2) to clarify imputation of missing start date for prior and concomitant medications
 
Update to Table 9 (Appendix 5) to add CTCAE grading for laboratory parameters analyzed per protocol

3 LIST OF ABBREVIATIONS AND DEFINITIONS OF TERMS

ACQ	Asthma Control Questionnaire
ADA	anti-drug antibody
AE	adverse event
AQLQ(S)+12	Standardized Asthma Quality of Life Questionnaire for 12 to 70 years
ASD	Asthma Symptom Diary
ATC	Anatomical Therapeutic Chemical
BMI	body mass index
CFB	change from baseline
CFB%	percentage change from baseline
CGI-I	Clinician Global Impression of Improvement
CGI-I/S	Clinician Global Impression of Improvement/Severity
CGI-S	Clinician Global Impression of Severity
CSR	Clinical Study Report
CTCAE	common terminology criteria for adverse events
DBP	diastolic blood pressure
ECG	electrocardiogram
eCRF	electronic case report form
EQ-5D-5L	European Quality of Life – 5 dimension 5 level questionnaire
EQ VAS	European Quality of Life visual analogue scale
ET	Early Termination
FAS	Full Analysis Set
FEV ₁	forced expiratory volume in 1 second
FeNO	fractional exhaled nitric oxide
ICS	inhaled corticosteroid

IFN- γ	interferon gamma
IL-6	interleukin 6
LABA	long-acting beta agonist
LIGHT	L ymphotoxin-like, exhibits I nducible expression, and competes with H erpes V irus G lycoprotein D for H erpesvirus E ntry M ediator, a receptor expressed by T lymphocytes
LFT	liver function test
MedDRA	Medical Dictionary for Regulatory Activities
NEA	non-eosinophilic asthma
PCI	potentially clinically important
PD	pharmacodynamic(s)
PGI-C	Patient Global Impression of Change
PGI-C/S	Patient Global Impression of Change/Severity
PGI-S	Patient Global Impression of Severity
PK	pharmacokinetic(s)
PT	preferred term
ppb	parts per billion
RAS	Randomized Analysis Set
SABA	short-acting beta agonist
SAP	statistical analysis plan
SAS	Safety Analysis Set
SBP	systolic blood pressure
SC	subcutaneous
SD	standard deviation
SG	Specific Gravity
SOC	system organ class

TEAE	treatmentemergent adverse event
TNF- α	tumor necrosis factor alpha
US	United States
VAS	visual analogue scale
WHO	World Health Organization
WHO-DD	World Health Organization Drug Dictionary

4 INTRODUCTION

The purpose of this SAP is to describe the framework for the reporting, summarization, and statistical analysis methodology of the safety and efficacy parameters measured throughout the study, applying principles and methodology per International Council for Harmonisation of Technical Requirements for Pharmaceuticals for Human Use (ICH) guidelines [1, 2]. It is based on Protocol AVTX-002-NEA-201, Version 5.0, dated 17 Oct 2022.

5 STUDY OBJECTIVES AND ENDPOINTS

Table 1. Study Objectives and Associated Endpoints

Objectives	Endpoints
Primary	
To assess the ability of AVTX-002 to improve asthma control in subjects with poorly controlled NEA	
Primary Endpoint: Proportion of subjects who experience any of the following asthma related events:
 
 • ≥ 6 additional reliever puffs of SABA (compared to baseline) in a 24-hour period on 2 consecutive days (where baseline SABA use is the average daily number of individual SABA puffs/inhalations taken by the subject during the 7 days preceding Visit 2) or, • increase in ICS dose ≥ 4 times than the dose at baseline (where baseline ICS dose is the dosage the subject received during the 30-day run-in period) or, • a decrease in peak flow of $\geq 30\%$ (compared to baseline) on 2 consecutive days of treatment (where baseline peak flow is the average of measurements in the 7 days preceding Visit 2) or, • an asthma exacerbation requiring the use of systemic corticosteroids (tablets, suspension, or injection) for at least 3 days or, • a hospitalization or emergency room visit because of an asthma exacerbation. 
Secondary Endpoints:
 
Change from baseline in FEV₁ at Weeks 2, 4, 6, 8, 12, and 14 Time to asthma related event Change from baseline in FeNO at Weeks 2, 4, 6, 8, 12, and 14 Change from baseline in ACQ at Weeks 2, 4, 6, 8, 12, and 14 Change from baseline in AQLQ(S)+12 at Weeks 2, 4, 6, 8, 12, and 14 Change from baseline in ASD score at Weeks 2, 4, 6, 8, 12, and 14 Change from baseline in EQ-5D-5L at Weeks 2, 4, 6, 8, 12, and 14 Change from baseline in PGI-C/S at Weeks 2, 4, 6, 8, 12, and 14 Change from baseline in CGI-I/S at Weeks 2, 4, 6, 8, 12, and 14 Incidence of SABA puffs/inhalations at Weeks 2, 4, 6, 8, 12, and 14

Secondary	
To assess the safety and tolerability of AVTX-002	Incidence of AEs, and changes from baseline in clinical laboratory tests, vital signs measurements, and physical examinations at Weeks 2, 4, 6, 8, 12, and 14
To evaluate biomarkers of PD activity and mechanism of action of AVTX-002	Change from baseline in serum soluble LIGHT levels at Weeks 2, 4, 6, 8, 12, and 14
To evaluate the immunogenicity of AVTX-002	Incidence of ADAs at Weeks 2, 4, 6, 8, 12, and 14
Exploratory	
To assess the ability of AVTX002 to improve asthma control in subjects with poorly controlled NEA who also have < 150 eosinophils/ μ L	Occurrence of an asthma related event in subjects with < 150 eosinophils/ μ L

Objectives	Endpoints
Exploratory (continued)	
To assess sputum soluble LIGHT levels and gene expression in a select subset of subjects	Change from baseline in sputum soluble LIGHT and gene expression (select subset of site/subjects only)
To evaluate inflammatory proteins including but not limited to: IL-6, IFN- γ , and TNF- α	Change from baseline in inflammatory proteins including but not limited to: IL-6, IFN- γ , and TNF- α
To evaluate the PK/PD relationship	PK/PD assessments
ACQ = Asthma Control Questionnaire; ADA = anti-drug antibody; AE = adverse event; AQLQ(S)+12 = Standardized Asthma Quality of Life Questionnaire for 12 to 70 years; ASD = Asthma Symptom Diary; CGI-I/S = Clinician Global Impression of Improvement/Severity; EQ-5D-5L = European Quality of Life – 5 dimension 5 level questionnaire; FeNO = fractional exhaled nitric oxide; FEV ₁ = forced expiratory volume in 1 second; ICS = inhaled corticosteroid; IFN- γ = interferon gamma; IL-6 = interleukin 6; LIGHT = Lymphotoxin-like, exhibits Inducible expression, and competes with Herpes Virus Glycoprotein D for Herpesvirus Entry Mediator, a receptor expressed by T lymphocytes; NEA = non-eosinophilic asthma; PD = pharmacodynamic(s); PGI-C/S = Patient Global Impression of Change/Severity; PK = pharmacokinetic(s); TNF- α = tumor necrosis factor alpha; SABA = short-acting beta agonist	

6 STUDY DESIGN CONSIDERATIONS

6.1 Study Design

This is a randomized, double-blind, placebo-controlled, Phase 2 study to evaluate the safety and efficacy of AVTX002 for the treatment of poorly controlled NEA. Upon confirmation of eligibility, subjects will complete a 30-day, stable therapy, run-in period with a LABA (salmeterol 50 µg twice daily) and an ICS (fluticasone, with starting dose at Investigator discretion). After the 30-day run-in is complete, subjects will be randomly assigned at the Baseline visit to receive either AVTX002 or placebo (1:1 ratio).

Fourteen days after randomization, subjects will discontinue salmeterol therapy (ie, at Visit 4). After an additional 14 days (ie, at Visit 5), subjects will taper fluticasone dose to 50%. After another 14 days (ie, at Visit 6), fluticasone use will be completely discontinued. The final visit will be Visit 9 (98 days after randomization).

Subjects will receive 3 doses of either AVTX002 or placebo (ie, at Visit 2, Visit 5, and Visit 7). AVTX002 or placebo will be administered by SC injection in the abdomen in a zone of 4 to 10 cm from the umbilicus, with the injection site rotated based on the number of syringes used. AVTX002 will be administered at a dose of 600 mg.

[figure not shown]
An adequate number of subjects will be enrolled to ensure approximately 80 subjects complete the study. Subjects who withdraw or are discontinued from the study or have poor study compliance may be replaced. The study will take place at approximately 25 study sites in the US.

All subjects will undergo efficacy, safety, PK/PD, and immunogenicity assessments as described in [Section 6.2](#), [Section 6.3](#), [Section 6.4](#), and [Section 6.5](#), respectively. Time points for all assessments are summarized in [Table 2](#).

The study schema is presented in [Figure 1](#) below.

Figure 1. Study Schema

Note: refer to [Section 8](#) for changes to numbering of assessment day, for purposes of reporting of study results. The assessment day as presented in [Figure 1](#) below, reflects the numbering as presented in the study protocol.

There is no interim analysis of data planned for this study.

6.1.1 Justification of Sample Size

The sample size in this study will be approximately 80 subjects, ie, 40 subjects per treatment arm, randomized in a 1:1 ratio.

The sample size estimate was based on the estimated proportions of subjects in the 2 treatment groups expected to have an asthma related event as defined by the primary endpoint. In a study of similar design with another asthma controller therapy, rates of 6% in the active group and 44% in the placebo group were observed [3]. If these estimates were used as is, then a study with 40 subjects per group would have over 95% power. Considering likely variations from the cited study, estimates of sample were assessed assuming a Type I error of 5% and the proportion of subjects with an asthma related event ranging from 30% to 50% in the placebo group and 5% to 8% in the active group. In the 20 such scenarios examined, only in the cases in which the difference between treatments gets below 23% does the power fall slightly below 80%. In the vast majority of cases examined the power is greater than 90%.

The overall event rate may be assessed in a blinded fashion when an adequate amount of subject followup has occurred. If this event rate is found to be much lower than assumed, a sample size reestimation may be performed.

6.2 Efficacy Measures

Time points for all assessments are summarized in [Table 2](#).

6.2.1 Asthma Related Events

The following are considered asthma related events:

- ≥ 6 additional reliever puffs of SABA (compared to baseline) in a 24-hour period on 2 consecutive days (where baseline SABA use is the average daily number of individual SABA puffs/inhalations taken by the subject during the 7 days preceding Visit 2)
- increase in ICS dose ≥ 4 times than the dose at baseline at any time post-baseline (where baseline ICS dose is the dosage the subject received during the 30-day run-in period)
- a decrease in peak flow of $\geq 30\%$ (compared to baseline) on 2 consecutive days of treatment (where baseline peak flow is the average of measurements in the 7 days preceding Visit 2)
- an asthma exacerbation requiring the use of systemic corticosteroids (tablets, suspension, or injection) for at least 3 days
- a hospitalization or emergency room visit because of an asthma exacerbation

The occurrence of each of the above asthma related events will be derived programmatically using different baseline definitions (where applicable), and from the source data as specified below:

Criterion to Meet for Asthma Related Event	Applicable Source Data	Baseline Definition
≥ 6 additional reliever puffs of SABA (compared to baseline) in a 24-hour period on 2 consecutive days *	ePRO Asthma Symptom Diary, ASD Morning and ASD Evening pages	The derivation whether a subject meets this criterion for an asthma related event will be performed using each of the 4 baseline values for mean daily number of SABA puffs/inhalations calculated according to Definitions 1 to 4 in Section 9.2
Increase in ICS dose ≥ 4 times than the dose at baseline at any time post-baseline	Prior and Concomitant Medications page of eCRF, coded appropriately so that ICS can be identified	ICS dose which the subject received during the 30-day run-in period
A decrease in peak flow of $\geq 30\%$ (compared to baseline) on 2 consecutive days of treatment	ePRO Asthma Symptom Diary, Peak Flow Diary page (before Peak Flow Diary page was available, this was collected as part of ASD Morning page)	The derivation whether a subject meets this criterion for an asthma related event will be performed using each of the 4 baseline values for mean peak flow rate calculated according to Definitions 1 to 4 in Section 9.2
An asthma exacerbation requiring the use of systemic corticosteroids (tablets, suspension, or injection) for ≥ 3 days **	Prior and Concomitant Medications page of eCRF, coded appropriately so that systemic corticosteroids can be identified	Not applicable
A hospitalization or emergency room visit because of an asthma exacerbation	Asthma exacerbation reported as SAE; in case SAE was not reported (ie, in case asthma exacerbation required only emergency room visit which consequently is not reported as SAE), the Investigator assessment in the eCRF of occurrence of an asthma related event is to be utilized as the source data	Not applicable

ICS = inhaled corticosteroid; SABA = short-acting beta agonist

- * This criterion may be met via 2 consecutive calendar days of assessments (ie, morning and evening diary entries for calendar date 1) plus morning and evening diary entries for the calendar date 2) or over a span of 3 consecutive calendar days (ie, evening diary entry for calendar date 1 and morning diary entry for calendar date 2 plus evening diary entry for calendar date 2 and morning diary entry for calendar date 3).
- ** In the case which use of systemic corticosteroids being administered for an asthma exacerbation is ongoing at the end of the study, the duration will be considered to be ≥ 3 days – as in clinical practice corticosteroid prescription including tapering usually last more than 3 days – and therefore the subject will be considered to have met this criterion for an asthma related event.
- ** Subjects being administered systemic corticosteroids for ≥ 3 days for a nonasthma event, will be considered to have met this criterion for an asthma related event, provided they have corresponding signs and symptoms of an asthma exacerbation. Also, subjects being administered a single dose of a longterm acting systemic corticosteroid (eg, dexamethasone) with a dose equivalent to a treatment of ≥ 3 days with other short to midterm systemic corticosteroids will be considered to have met this criterion for an asthma related event. Such cases will be confirmed by the sponsor as having met the criterion for an asthma related event or not.

In addition, an Investigator assessment of the occurrence of an asthma related event is recorded in the eCRF at each visit during the course of the study.

Time to first asthma related event will be measured in days as follows:

- Subjects with an asthma related event (censor = 0): the first day of the event above denotes the first day the protocol defined criteria associated with the asthma related event occurred (eg, for peak flow, the first of 2 days a decrease of $\geq 30\%$ occurred, or for systemic corticosteroid use, the start of the qualifying medication), ie, time to event is calculated as follows:

$$(start\ date\ of\ first\ asthma\ related\ event - date\ of\ first\ administration\ of\ study\ drug) + 1$$

For subjects that do NOT have an asthma related event (censor = 1), the day of the last subject visit denotes the day of censoring, ie, time to censoring is calculated as follows:

$$(date\ of\ last\ subject\ visit - date\ of\ first\ administration\ of\ study\ drug) + 1$$

Furthermore, an annual asthma related event rate will be calculated for each treatment group as follows (for exploratory reasons):

$$365.25 * \left(\frac{\text{total number of asthma related events within the treatment group}}{\text{total duration of study participation with the treatment group [days]}} \right)$$

where total duration of study participation within treatment group (days) is the sum of $(date\ of\ last\ subject\ visit - date\ of\ first\ administration\ of\ study\ drug) + 1$ for all subjects.

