#### 11.2.2.3 Serious Adverse Event Definition

An SAE is any untoward medical occurrence, whether considered to be related to investigational product or not, that at any dose:

- **Results in death.**
- **Is life-threatening.**

*NOTE: The term "life-threatening" in the definition of "serious" refers to an event in which the subject was at risk of death at the time of the event; it does not refer to an event which hypothetically might have caused death if it were more severe.*

- **Requires inpatient hospitalization or prolongation of existing hospitalization.** *NOTE: Inpatient hospitalization is defined as 24 hours in a hospital or an overnight stay. An elective hospital admission to treat a condition present before exposure to the test drug, or a hospital admission for a diagnostic evaluation of an AE, does not qualify the condition or event as an SAE. Further, an overnight stay in the hospital that is only due to transportation, organization, or accommodation problems and without medical background does not need to be considered an SAE.*
- Results in persistent or significant disability/incapacity.

- **Is a congenital anomaly.**

*NOTE: A congenital anomaly in an infant born to a mother who was exposed to the investigational product during pregnancy is an SAE. However, a newly diagnosed pregnancy in a subject that has received an investigational product is not considered an SAE unless it is suspected that the investigational product(s) interacted with a contraceptive method and led to the pregnancy.*

- **Is an important medical event.**

*NOTE: Medical and scientific judgment should be exercised in deciding whether it is appropriate to consider other situations serious, such as important medical events that may not be immediately life-threatening or result in death or hospitalization but may jeopardize the subject or may require intervention to prevent one of the other outcomes listed in the definition above. Examples of such events are intensive treatment in an emergency room or at home for allergic bronchospasm, blood dyscrasias or convulsions that do not result in hospitalization, or development of drug dependency or drug abuse.*

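### SAP 6.2.1 sources the hospitalization/ER criterion from asthma SAE reports without requiring that the SAE involved a hospitalization or ER visit, so the program can count a criterion that was not met

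*SAP*

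**What the plan says.** SAP 6.2.1 defines the fifth criterion as "a hospitalization or emergency room visit because of an asthma exacerbation". The table in that section sets a source beside each criterion. For this one the cell begins "Asthma exacerbation reported as SAE; in case SAE was not reported". A parenthesis then explains when no SAE is expected: "in case asthma exacerbation required only emergency room visit which consequently is not reported as SAE". In that case "the Investigator assessment in the eCRF of occurrence of an asthma related event is to be utilized as the source data". The SAP adds that "an Investigator assessment of the occurrence of an asthma related event is recorded in the eCRF at each visit during the course of the study".

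Protocol 11.2.2.3 sets what is serious. Death, a life-threatening event or an important medical event qualifies without admission, and one example of the last is "intensive treatment in an emergency room or at home for allergic bronchospasm". Inpatient hospitalization needs 24 hours or an overnight stay. A "hospital admission for a diagnostic evaluation of an AE, does not qualify the condition or event as an SAE".

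SAP 10.6.1 bases the primary analysis on the programmed derivation. SAP 10.6 lists discordance between the program and the investigator, but no rule lets that listing change the result.

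**The concern.** The criterion concerns a place of care. The source concerns a regulatory classification. The two overlap without coinciding, and the cell has no filter on why the event was serious. A programmer who takes it literally flags the criterion for every asthma exacerbation in the SAE data, including one managed with no hospital or ER contact.

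The parenthesis suggests that the cell treats SAE status as equivalent to admission, since it concludes that an ER-only visit is not an SAE. The protocol gives intensive ER treatment as an SAE example.

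At stake are the primary comparison and the separate row for this criterion that SAP 10.6.1 requires. The same derivation also feeds the log-rank comparison and annual event rate (SAP 10.6.2) and the repeat analyses in SAP 10.6.3.

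**Working it through.** **1. Criterion against source, by type of event.**

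| Asthma exacerbation | Criterion met? | Source as written | Result |
|---|---|---|---|
| Inpatient stay of 24 h or overnight | Yes | SAE | Counted, correct |
| ER only, reported as SAE | Yes | SAE | Counted, correct |
| ER only, not an SAE | Yes | Investigator fallback | Counted, correct |
| SAE on another ground, no hospital or ER contact | No | SAE | Counted if followed literally: over-count |
| Short or diagnostic admission, not an SAE | Yes | Depends on how the fallback is read | Counted or missed |

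Only the last two rows are in doubt. The conflict over ER visits affects rows 2 and 3, where one source or the other counts the subject.

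**2. Does another provision stop the over-count?** The investigator assessment is consulted only when no SAE was reported, so it cannot overrule an SAE. Sponsor confirmation is written for ambiguous corticosteroid cases but not for this criterion. Protocol 11.1.1 expects some exacerbations to fall outside the endpoint definition and sends them to the AE data. If one of those is judged serious, the SAP source brings it back in as an endpoint event.

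**3. The fallback.** Its opening condition is simply that no SAE was reported, which covers the last row. The parenthesis starts with 'ie', which normally restates rather than illustrates. Read that way, the fallback covers ER-only visits alone. Protocol 11.1.1 does not require endpoint events to be recorded as AEs unless serious, so a non-SAE admission might then leave no AE record.

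**4. Planning figure.** Inputs from SAP 6.1.1: 40 per arm, 44% v 6%, Type I error 5% (two-sided assumed).

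- Pooled SE under the null: √(2 × 0.25 × 0.75/40) = 0.0968.
- Unpooled SE: √(0.44 × 0.56/40 + 0.06 × 0.94/40) = 0.0870.
- Power: Φ[(0.38 − 1.96 × 0.0968)/0.0870] = Φ(2.19) = 98.6%.
- With the unpooled Wald test: 99.2% uncorrected, 98.3% corrected.

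The stated figure of over 95% reproduces and does not depend on this point.

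**5. One subject.** Each is 1/40 = 2.5 points. Corrected Wald: z = (|d| − 1/40)/√(p₁q₁/40 + p₂q₂/40), with q = 1 − p.

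| Events, active v placebo | z | p |
|---|---|---|
| 2 v 10 | 2.28 | 0.022 |
| 3 v 10 | 1.87 | 0.061 |
| 3 v 11 | 2.13 | 0.033 |

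For 3 v 10: (0.175 − 0.025)/√(0.0046875 + 0.0017344) = 0.150/0.0801 = 1.87. One over-counted active subject moves row 1 to row 2, and one over-counted placebo subject moves row 2 to row 3. Without the correction, which SAP 10.6.1 also plans, 3 v 10 gives p = 0.029. Near the planning rates, 2 v 18 gives z = 4.37 and 3 v 18 gives z = 3.93 (p = 0.0001), so nothing changes.

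**6. Range under assumed misclassification.** The documents give no rate. Suppose a share f of non-event subjects in both arms were wrongly counted (pooled test):

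| f | Power, 44% v 6% | Power, 30% v 8% |
|---|---|---|
| 0 | 98.6% | 71.6% |
| 2.5% | 97.5% | 65.9% |
| 5% | 96.0% | 60.6% |
| 10% | 92.0% | 51.3% |

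At f = 2.5% and 44% v 6%, the expected number wrongly counted is 0.025 × (22.4 + 37.6) = 1.5 subjects in the trial. The larger values of f bound the effect and are not a forecast.

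**The case against.** The strongest reply is that the SAE wording sits in a source column while the criterion column still requires a hospitalization or ER visit. The corticosteroid row is built the same way: it names the medications page, and nobody would count every steroid record. On that view the cell says where to look and sets no new criterion. This has force. A reader might infer that the SAP declares every asthma SAE to be proof of a hospital or ER visit, and it contains no such explicit rule. But the corticosteroid row's criterion can be tested from drug, dates and duration, whereas this cell names no field that would separate a hospital or ER event from other SAEs, and its aside about ER visits suggests that the distinction was overlooked.

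A reader might also infer that the criterion errs equally in both directions, or that the ER conflict loses events. The documents do not support either. The fallback's opening words admit any exacerbation without an SAE, the investigator assesses at each visit, and the listing in SAP 10.6 shows the qualifying specification. A miss needs the narrow reading of the parenthesis. Even then it is confined to short or diagnostic admissions, because elective or transport-related stays are generally not due to an exacerbation, and a short stay may begin in the ER.

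Finally, the over-count changes the composite only if the subject meets none of the SABA, ICS, peak-flow or corticosteroid criteria. A severe home-treated exacerbation would plausibly meet one of them. That stands, and it limits the size of the effect.

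**Conclusion.** The over-count is real if the cell is programmed as written: an asthma SAE with no hospital or ER contact would be recorded under a criterion it does not meet. The under-count is conditional on a restrictive reading of the parenthesis. The conflict with the protocol's ER example is a drafting error that misses no one by itself.

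The expected effect on the primary result is small. It rests on the judgement that such SAEs are rare and that most of these subjects would meet another criterion; the documents give no rate for either. The p-values show only that one subject can matter at a chosen boundary, as under any endpoint rule, and at the planning rates one subject does not matter. The row for this criterion in the SAP 10.6.1 table can be wrong even when the composite is not. The change is worth making because this is a primary-endpoint derivation and the correction is cheap.

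**What to change.** In the SAP 6.2.1 source cell for this criterion:

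- Count an asthma-exacerbation SAE only where the record shows a hospitalization or ER visit. Use the seriousness criterion if the SAE form holds it, and otherwise the investigator's specification of the event. The documents available do not show whether that field is collected, so this must be checked.
- Also count any hospitalization or ER visit for asthma recorded in the investigator's eCRF assessment, whether or not it was an SAE.
- Delete the clause that infers from an ER-only visit that no SAE is reported.

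The cost is a short text edit and a minor programming change. One consequence should be accepted openly: a severe asthma SAE with no hospital or ER contact would count only if it meets another criterion, as the protocol's endpoint definition already implies.
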